12.2.2. Patient Disposition

A detailed description of patient disposition will be provided. It will include a summary of the number and percentage of patients entered into the study, enrolled in the study, and treated as well as number and percentage of patients discontinuing (overall and by reason for discontinuation) from both study treatment and study itself. A summary of all important protocol violations will be provided.

For the purpose of clinical trial registry reporting, patients who have died or are still in the study but off treatment at primary data base lock will be considered a completer. Those who withdrew

consent for all procedures, including follow-up, or were lost to follow up, will be considered as early discontinuers. Patients who remain on treatment will be counted as continuing treatment.

12.2.3. Patient Characteristics

Patient demographics including age, sex, screening height and weight, and screening body surface area will be listed and summarized using descriptive statistics.

Baseline disease characteristics will be summarized, by presenting frequency counts and percentages, such as pathological diagnosis (histological or cytological) and disease grade.

Prior disease-related regimens will also be listed and summarized by regimen, detailing individual therapies within each regimen (Section [12.2.4.1](#)).

Other patient characteristics will be summarized as deemed appropriate.

12.2.4. Concomitant Therapy

Concomitant medications will be summarized for the safety population using generic names and class of drugs using standard dictionary, such as the WHO drug dictionary.

Enzyme-inducing and non-enzyme inducing anti-epileptic drug treatments will be collected and reported separately.

Steroid drug intake will be collected and reported separately.

12.2.4.1. Prior Regimens

Listings of patients' prior regimen will be provided, such as chemoradiation with TMZ. Listings will include regimen number indicating which different therapies and/or types of therapies are included in the same regimen. The numbers and percentages of patients reporting prior regimens will be provided.

12.2.4.2. Postdiscontinuation Regimens

Listings of patients reporting postdiscontinuation therapies will be provided.

Bevacizumab treatment after poststudy drug discontinuation will be listed and included in the OS analyses to detect any potential influence on OS.

Listings will include regimen number indicating which different therapies and/or types of therapies are included in the same regimen. The numbers and percentages of patients reporting postdiscontinuation regimens will be provided overall.

12.2.5. Treatment Compliance

The number of dose omissions, reductions, delays, number of cycles received, and dose intensity will be summarized for all treated patients per treatment arm. Summarized data will be provided for the treatment period.

Treatment compliance within a cycle means that the patient has taken their allocated treatments as prescribed for that cycle (see Section [9.1](#)). (This is distinct from dose intensity which

calculates the amount of drug taken per cycle compared to the dose the patient was initially assigned at the start of the study and is defined in Section 12.2.10).

Treatment compliance information for LY2157299 and placebo will be collected through both pill counts and by the site querying the patient at the end of each cycle for each patient. The number of tablets taken relative to the number expected to be taken will be summarized by cycle and treatment arm.

12.2.6. Primary Outcome and Methodology

Overall survival (OS) duration is measured from the date of randomization to the date of death from any cause. For each patient who is not known to have died as of the data-inclusion cut-off date for a particular analysis, OS will be censored for that analysis at the date of last contact prior to the data inclusion cutoff date (contacts considered in the determination of last contact date include AE date, lesion assessment date, visit date, and last known alive date).

A method of analysis for comparing OS between the treatment arms will use a Bayesian exponential-likelihood model with possibly a hierarchical random-effects distribution on treatment effects. The model incorporates historical data from 2 studies (Study H6Q-MC-JCBF [data on file and Wick et al. 2010a]; Batchelor et al. 2010a) with a lomustine plus placebo arm to augment the prospective control arm data. If the Bayesian posterior probability of superiority of LY2157299 plus lomustine therapy over lomustine plus placebo therapy (control) (ie, HR **CCI** [REDACTED]), then it will be concluded that the combination arm is superior. A similar Bayesian analysis will be carried out to provide 90% predictive intervals of the HR between the lomustine plus placebo and LY2157299 monotherapy. See [Attachment 10](#) for more details.

12.2.7. Additional Efficacy Analyses

Overall survival (OS) is the primary outcome of interest and the primary analysis is as described above.

Overall survival (OS) and OS rate at 12 months will be summarized by treatment arm using Kaplan-Meier estimates of the median survival times (including 95% CIs) to inform assumptions for use in future trial planning (Kaplan and Meier 1958). Additional exploratory analyses using proportional hazards models to control for other factors may be performed, including, but not limited to, adding a covariate indicating the extent of lomustine exposure, PD marker assessment of the tumor tissue, the known influence factors, such as age, PS, and primary or secondary GB and whether patients had poststudy treatment with bevacizumab.

The following secondary efficacy parameters will be summarized for each treatment group:

- PFS distribution parameters and PFS rate
- ORR

Progression-free survival and PFS rate will be summarized (at **CCI** [REDACTED]) using Kaplan-Meier estimates of the median survival times (including 95% CIs) to inform assumptions for use in future trial planning (Kaplan and Meier 1958). Estimates of HRs between

the 3 arms will also be provided. Additional exploratory analyses using proportional hazards models to control for other factors may be performed.

Overall response rate (ORR) and, additionally, disease control rate given the risk of pseudo progression, will be estimated by dividing the total number of responders ([CR or PR] or [CR or PR or SD]) by number of randomly assigned patients. Exact 95% CIs for each treatment arm will be provided.

Additional analyses may be carried out to judge the influence of any patients who did not meet enrollment criteria but were inadvertently enrolled and continued on treatment after obtaining approval from the sponsor and/or patients who have continued treatment after objective disease progression (see Section 7.3.1). A subanalysis will be conducted by excluding such patients to determine their influence on the final study results.

12.2.8. Pharmacokinetic/Pharmacodynamic Analyses

Pharmacokinetic analyses will be conducted on patients who have received at least 1 dose of the investigational product and have had samples collected.

Population-based PK analysis will be performed using sparse PK data with validated PK software programs (for example, NONMEM). The version of any software used for the analysis will be documented and the program will meet the Lilly requirements of software validation.

Pharmacodynamic data from all patients undergoing PD assessments will be analyzed. Pharmacodynamic data will be documented in the study report by dose, exposure, and time from dose. Exploratory PK/PD analyses will be conducted as data become available to determine the relationship between exposure and PD effect. The PK/PD data will be analyzed using validated software programs (for example, WinNonlin and NONMEM). The version of software used for the analysis will be documented and will meet the Lilly requirements of software validation.

12.2.9. Health Outcome Analyses

Patients with at least baseline and 1 post-baseline assessment will be included in the analyses. Compliance with completing the questionnaires will be summarized at the group-level at each assessment period (defined as the number of completed questionnaires/number expected questionnaires given those that are still on study).

Each health outcome parameter will be reported independently. Relationships (predictors or prognostic) among these parameters and with other clinical parameters such as PS, OS, and disease assessments (based on MRI) may be explored.

12.2.9.1. Neurocognitive Function

Each neurocognitive test will be converted to a standardized score (mean = 0, SD = 1) using published healthy control data. Data will be summarized for each assessment period and change over time will be explored. Differences in neurocognitive progression will be assessed between arms using Cox proportional hazards regression.

Further analyses will be specified in the SAP.

12.2.9.2. MD Anderson Symptom Inventory – Brain Tumor Module

The MDASI-BT will be analyzed as described in the MDASI user manual. Data will be summarized for each assessment period and compared between arms. This summary will include mean, standard deviation, median, minimum, maximum, and change from baseline (including time to worsening of symptoms). A minimally important difference of 1.2 (as defined in the MDASI user manual) will be used in the time to worsening analyses. The MDASI-BT will be reported as core symptoms, brain tumor symptoms, symptom interference, and symptom groupings (affect, cognition, focal neurologic deficit, treatment-related symptoms, generalized/disease status symptoms, and gastrointestinal symptoms).

Further analyses will be specified in the SAP.

12.2.10. Safety Analyses

All safety summaries and analyses will be based upon the safety population as defined in Section 12.2.1.

Overall exposure to study drug, the numbers of patients completing each cycle, and the dose intensity will be summarized using descriptive statistics. The number of patients with any dose adjustment will be presented for entire treatment period as well as for each cycle. The number of patients with dose reductions, dose delays, or dose omissions will also be summarized, as will the reasons for dose adjustments.

Common Terminology Criteria for Adverse Events (CTCAE) version 4 will be used to report AEs. The MedDRA Version 14.0 (or higher) will be used when reporting AEs by MedDRA terms. The MedDRA lower level term (LLT) will be used in the treatment-emergent computation.

A TEAE is defined as an event that first occurred or worsened in severity after baseline, based on the MedDRA LLT and CTCAE severity grade. This means that any episode of the same AE with the same grade as at baseline that starts after the first dose of study treatment will not be defined as treatment emergent, even if now considered possibly drug related.

An overall summary of AEs will be provided for AEs deemed by the investigator to be possibly related to study medication, and repeated for events regardless of study drug causality. Incidence rates of these events will be compared between treatment arms using Fisher's exact test. These analyses and summaries will be repeated for TEAEs.

The TEAEs will be summarized separately for both MedDRA and CTCAE dictionaries, by their respective System Organ Class (SOC) terms and by decreasing frequency of their respective preferred term (PT) within SOC.

The number of evaluable patients who experienced a TEAE, SAE, AE related to study drug, died, or discontinued from the study due to an AE will be summarized by treatment.

The CTCAEs, separated by those defined as laboratory and non-laboratory CTCAEs, will be summarized by CTCAE term and maximum CTCAE grade, including the total for maximum Grade 3 and 4. These summaries will be provided for events regardless of study drug causality,

and repeated for events deemed by the investigator to be possibly related to study medication. These summaries will be repeated for TEAEs.

A calculated CTCAE grade will be provided for all laboratory results which can be used independently of clinical judgment to determine a CTCAE severity grade. These will be summarized by CTCAE grade in a separate table, linking the CTCAE term to the laboratory term in question.

Reasons for death will be summarized separately for on-therapy, within 30 days of last dose of study drug and during the long-term follow-up periods. The SAEs will be summarized by MedDRA and CTCAE PT.

Hospitalizations and transfusions during the study treatment period or during the 30-day postdiscontinuation follow-up period will be summarized by treatment group.

12.2.10.1. Cardiac Safety Analyses

Refer to [Attachment 1](#) and [Attachment 2](#) for timing of ECGs, ECG chemistry, and ECHOs.

Echocardiography/Doppler assessments will be done as outlined in [Attachment 6](#).

Baseline ECGs are ECGs performed either during screening or predose during the study. Changes in QT from baseline, delta QT, will be calculated by subtracting the respective reading taken at the same nominal time during screening from the reading taken after LY2157299 dosing on specified days in [Attachment 1](#). Similarly, changes in RR from baseline, delta RR, will be calculated. Delta QT will then be analyzed using a linear mixed-effects model (Dmitrienko and Smith 2003).

In addition, listings and summaries of outlying corrected QT intervals (QTc [QTc – Bazett's correction (QTcB) and QTc – Fridericia's correction (QTcF)]) will be provided for each scheduled time point.

If data warrant, additional exploratory analyses may be conducted using appropriate modeling techniques.

The ECG chemistry laboratory values will be listed and summarized separately from other laboratory values.

Individual patient listings and summaries by treatment arm will be provided for all echocardiograph variables. Shift tables indicating maximum changes from baseline will be provided for qualitative variables and absolute and/or percent change from baseline for quantitative variables.

12.2.11. Subgroup Analyses

There are no planned subgroup analyses. However, exploratory analyses may be performed to generate hypotheses about the efficacy of study therapy in certain subgroups to be tested in future clinical trials.

[figure not shown]
12.2.12. *Interim Analyses*

CC1 interim assessments are planned:

The combination arm or LY2157299 monotherapy arm could be considered futile if, after ~~CC1~~ patients have completed 3 cycles, the posterior probability is less than 10% that the HR for OS of combination arm or LY2157299 arm versus lomustine arm is less than ~~CC1~~.

See [Attachment 10](#) for the operating characteristics for this analysis.

See [Attachment 10](#) for the operating characteristics for this analysis.

The plan is to continue enrolling patients into the study during each interim analysis unless ongoing safety reviews have raised safety concerns.

The safety/tolerability and efficacy results from the interim analyses will be reviewed only by an internal Assessment Committee consisting of the Lilly Medical Director, a Lilly CRP not in contact with study sites, a Lilly statistician, and a PK scientist, if needed. The assessment committee members will review unblinded safety and/or efficacy data at each interim analysis to determine whether there are sufficient safety or futility concerns to justify the termination of a

study treatment arm. Results of the interims will not be communicated to the study sites, unless the interim analysis shows evidence of harm.

Unblinding details are specified in the unblinding plan section of the SAP.

13. Informed Consent, Ethical Review, and Regulatory Considerations

13.1. Informed Consent

The investigator is responsible for ensuring that the patient understands the potential risks and benefits of participating in the study, including answering any questions the patient may have throughout the study and sharing in a timely manner any new information that may be relevant to the patient's willingness to continue his or her participation in the trial.

The ICF will be used to explain the potential risks and benefits of study participation to the patient in simple terms before the patient is entered into the study, and to document that the patient is satisfied with his or her understanding of the risks and benefits of participating in the study and desires to participate in the study.

The investigator is responsible for ensuring that informed consent is given by each patient or legal representative. This includes obtaining the appropriate signatures and dates on the ICF prior to the performance of any protocol procedures and prior to the administration of study drug.

13.2. Ethical Review

Lilly or its representatives must approve all ICFs before they are submitted to the ERB and are used at investigative sites(s). All ICFs must be compliant with the International Conference on Harmonisation (ICH) guideline on GCP.

Documentation of ERB approval of the protocol and the ICF must be provided to Lilly before the study may begin at the investigative site(s).

Any member of the ERB who is directly affiliated with this study as an investigator or as site personnel must abstain from the ERB's vote on the approval of the protocol.

The study site's ERB(s) should be provided with the following:

- the current IB or package labeling and updates during the course of the study
- ICF
- relevant curricula vitae

13.3. Regulatory Considerations

This study will be conducted in accordance with:

- 1) consensus ethics principles derived from international ethics guidelines, including the Declaration of Helsinki and Council for International Organizations of Medical Sciences (CIOMS) International Ethical Guidelines
- 2) the ICH GCP Guideline [E6]
- 3) applicable laws and regulations.

The investigator or designee will promptly submit the protocol to applicable ERB(s).

All or some of the obligations of the sponsor will be assigned to a TPO.

An identification code assigned by the investigator to each patient will be used in lieu of the patient's name to protect the patient's identity when reporting AEs and/or other trial-related data.

13.4. Investigator Information

Physicians with a specialty in oncology will participate as investigators in this clinical trial.

13.4.1. Protocol Signatures

After reading the protocol, each principal investigator will sign the protocol signature page and send a copy of the signed page to a Lilly representative.

Attachment 1. JBAL Study Schedule

Study Schedule for Protocol H9H-MC-JBAL – Prestudy and Cycle 1

Cycle	Prestudy			Cycle 1								Comments
	Relative Day	≤28	≤14	≤7	1	3	7±2	12±2	14	15	16	26±2
Treatment												
Lomustine						X						
LY2157299 monohydrate or matched placebo				X	X	X	X	X				CCI
Procedures												
Informed consent	X											
Medical history		X										
Pregnancy test		X										CCI
Physical Examination		X		X								
Vital signs (heart rate, blood pressure)		X		X								
CTCAE		X		X								
Concomitant medications		X		X								

Cycle	Prestudy			Cycle 1							Comments	
	Relative Day	≤ 28	≤ 14	≤ 7	1	3	7 ± 2	12 ± 2	14	15	16	
Relative Day	≤ 28				1	3	7 ± 2	12 ± 2	14	15	16	26 ± 2
Within a Cycle												
ECOG performance status		X		X								
Health outcome measures		X									X	
Imaging Procedures												
Echocardiography with Doppler		X										
Radiological tumor assessment		X										
Chest CT scan or chest MRI		X										
Laboratory/Diagnostic Tests												
PFT			X									
ECG		X		X	X			X	X		X	
Troponin I and BNP			X								X	
Hematology			X								X	
Urinalysis			X								X	
Fox P3			X									

CCI

Cycle	Prestudy			Cycle 1							Comments	
	Relative Day	≤ 28	≤ 14	≤ 7	1	3	7 ± 2	12 ± 2	14	15	16	
Relative Day	≤ 28	≤ 14	≤ 7		1	3	7 ± 2	12 ± 2	14	15	16	26 ± 2
Serum chemistry			X								X	
ECG chemistry		X		X	X			X	X			
Serum hs-CRP			X									X
PK sampling				X	X			X	X	X		
CSF												
MAP				X			X					
Affymetrix				X								
Whole blood for PGx		X										
Whole blood/plasma				X								
Tumor tissue		X										

Study Schedule for Protocol H9H-MC-JBAL – Cycles 2, 5, 8, 11

Cycle	Cycles 2, 5, 8, 11					Comments
Relative Day Within a Cycle	1±2	6±2	12±2	21±2	26±2	
Treatment						
Lomustine				X		
LY2157299 monohydrate or matched placebo	X	X	X			
Procedures						
Physical examination	X		X			
Vital signs (heart rate, blood pressure)	X					
CTCAE	X					
Concomitant medications	X					
ECOG performance status	X					
Health outcome measures					X	
Echocardiography with Doppler					X	
ECG					X	
Tropionin I and BNP					X	
Hematology					X	
Urinalysis					X	
Fox P3					X	
Serum chemistry					X	

CCI

ECG chemistry					X	
Cycle	Cycles 2, 5, 8, 11					Comments
Relative Day Within a Cycle	1±2	6±2	12±2	21±2	26±2	
Serum hs-CRP					X	
Radiological tumor assessment					X	CCI
MAP			X			
Affymetrix					X	

Study Schedule for Protocol H9H-MC-JBAL – Cycles 3, 6, 9, 12

Cycle	Cycles 3, 6, 9, 12				Comments
Relative Day Within a Cycle	1±2	6±2	12±2	26±2	
Treatment					
Lomustine					
LY2157299 monohydrate or matched placebo	X	X	X		
Procedures					
Physical examination	X				
Vital signs (heart rate, blood pressure)	X				
CTCAE	X				
Concomitant medications	X				
ECOG performance status	X				
Health outcome measures				X	
Echocardiography with Doppler				X	
ECG				X	
PFT				X	
Troponin I and BNP				X	
Hematology				X	
Fox P3				X	

CCI

Cycle	Cycles 3, 6, 9, 12				Comments
Relative Day Within a Cycle	1±2	6±2	12±2	26±2	
Serum chemistry				X	
ECG chemistry				X	
Serum hs-CRP				X	
Radiological tumor assessment				X	
Chest CT scan or chest MRI				X	
MAP				X	
Affymetrix				X	

CCI

Study Schedule for Protocol H9H-MC-JBAL – Cycles 4, 7, 10, Visit 801, Follow-Up

Cycle	Cycles 4, 7, 10				Visit 801	Follow Up	Comments
Relative Day Within a Cycle	1±2	6±2	12±2	26±2			
Treatment							
Lomustine		X					
LY2157299 monohydrate or matched placebo	X	X	X				
Procedures							
Physical examination	X				X		
Vital signs (heart rate, blood pressure)	X				X		
CTCAE	X				X		
Concomitant medications	X				X		
ECOG performance status	X				X		
Health outcome measures				X	X		
Echocardiography with Doppler				X	X	X	
ECG				X	X	X	
Troponin I and BNP				X	X		

Hematology				X	X	CC1	
Cycle	Cycles 4, 7, 10				Visit 801	Follow Up	Comments
Relative Day Within a Cycle	1±2	6±2	12±2	26±2			
Urinalysis				X	X		
Serum chemistry				X	X		
ECG chemistry				X	X	X	
Fox P3				X			
Serum hs-CRP				X			
Radiological tumor assessment				X			
MAP				X			
Affymetrix				X			

Abbreviations: BNP = brain natriuretic peptide; COWA = Controlled Oral Word Association; CSF = cerebrospinal fluid; CT = computed tomography; CTCAE = Common Terminology Criteria for Adverse Events; ECG = electrocardiogram; ECOG = Eastern Cooperative Oncology Group; GB = glioblastoma; hs-CRP = high-sensitivity C-reactive protein; HVLT-R = Hopkins Verbal Learning Test – Revised; MAP = multi-analyte panel; MDASI-BT = MD Anderson Symptom Inventory-Brain Tumor; MRI = magnetic resonance imaging; PFT = pulmonary function test; PGx = pharmacogenetics; PK = pharmacokinetic; TGF-β = transforming growth factor – beta.

Study Schedule for the continued access period only, Protocol H9H-MC-JBAL

Cycle	Continued Access ^a Visit 501-5XX				Follow-Up ^b Visit 801	Comments
	1±2	6±2	12±2	26±2		
Relative Day Within a Cycle						
Treatment						
Lomustine		X				
LY2157299	X	X	X			
Procedures						
Physical examination	X				X	
Vital signs (heart rate, blood pressure)	X				X	
CTCAE	X				X	
Echocardiography with Doppler				X	X	
ECG				X	X	
Troponin I and BNP				X	X	
ECG chemistry				X	X	
Serum hs-CRP				X		

Abbreviations: BNP = brain natriuretic peptide; CTCAE = Common Terminology Criteria for Adverse Events; ECG = electrocardiogram; hs-CRP = high-sensitivity C-reactive protein.

a No follow-up procedures will be performed for patients who withdraw informed consent unless he or she has explicitly provided permission and consent.

b Continued access follow-up begins 1 day after the patient and the investigator agree that the patient will no longer continue treatment in the continued access period and lasts approximately [30] days.

Note: Efficacy assessments will be done at the investigator's discretion based on the standard of care.

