8.1. Summary of Study Design

Study JBAL is a 3-arm, randomized, multicenter, global, Phase 2 study of LY2157299 monotherapy or LY2157299 plus lomustine therapy compared to lomustine plus LY2157299-matched placebo therapy in patients with relapsed or progressed GB. **CCI**

■ patients will be entered with the aim of randomizing **CCI** patients in a **CCI** fashion to LY2157299 monotherapy or LY2157299 plus lomustine therapy or lomustine plus LY2157299-matched placebo therapy (see Section 12.1). **Figure JBAL.8.1** illustrates the study design. Patients and investigators will be blinded to the LY2157299 or placebo assignment for those patients who receive lomustine. One cycle is defined as 28 days in all treatment arms and constitutes 14 days on/14 days off of LY2157299/LY2157299-matched placebo.

Figure JBAL.8.2 illustrates an overview of the first 4 cycles for each treatment arm.

[figure not shown]

Figure JBAL.8.1. Illustration of study design for Protocol H9H-MC-JBAL.

[figure not shown]

Figure JBAL.8.2. Illustration of LY2157299 and lomustine administration for the first 4 treatment cycles in Protocol H9H-MC-JBAL.

In Cycle 1, lomustine will be given after LY2157299 or placebo has been given for 7 days (on Day 7 of Cycle 1). After the first dose, lomustine will then be given once every 6 weeks to those patients assigned to either the LY2157299 plus lomustine or lomustine plus placebo treatment groups. The planned treatment with lomustine will be limited to 6 administrations. For details, see Section 9.1.

[figure not shown]
The primary comparison for efficacy is to compare OS between the LY2157299 plus lomustine therapy and lomustine plus placebo therapy. Additional endpoints (eg, PFS, response rate) will be estimated.

Further analyses will be carried out to estimate efficacy and safety endpoints for LY2157299 monotherapy and LY2157299 plus lomustine therapy. This secondary analysis will provide an assessment of whether the monotherapy treatment with LY2157299 is as active as lomustine alone. At the same time, this design will offer additional information whether LY2157299 monotherapy has a toxicity profile that warrants further investigation.

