9.4.1.1. Lomustine Hematologic Adverse Events

Blood counts should be monitored weekly and repeat doses of lomustine should be given every 6 weeks due to possible delayed hematotoxicity. Dose adjustments at the start of a subsequent cycle of therapy will be based on the lowest platelet and ANC (nadir) counts. A repeat dose of lomustine should not be given until ANC and platelet counts return to baseline levels or Grade 1, which usually occurs within 6 weeks.

Any patient who requires a dose reduction due to hematologic AEs will continue to receive a reduced dose for the remainder of the study. Any patient with 2 prior dose reductions, who experiences a toxicity that would cause a third dose reduction, must be discontinued from

lomustine therapy. A patient who, for any reason, cannot be administered lomustine for 12 weeks from the last lomustine dose, must be discontinued from *lomustine therapy*.

If either of the foregoing occur and, in the judgment of the treating physician, it is felt that the patient is benefiting from the treatment and after approval by the Lilly CRP, the patient may continue LY2157299 or placebo treatment, until disease progression or additional unacceptable toxicity occurs.

Treating physicians at the investigative sites will dose adjust lomustine based upon the following suggested guidelines (refer to [Table JBAL.9.1](#)) or best institutional practices:

Table JBAL.9.1. Dose Adjustment Guide for Lomustine Based on Nadir Hematologic Values for Preceding Cycle

Nadir After Prior Dose		Percentage of Prior Dose to be Given
ANC ($\times 10^9/L$)	Platelets ($\times 10^9/L$)	
LLN – 1.5	>75	100%
1.5 – 1.0	25 – 75	70%
<1.0	<25	50%

Abbreviations: ANC = absolute neutrophil count; LLN = lower limit of normal.

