9.5. Continued Access to Study Drug

The intended treatment for lomustine is 6 doses, each given 6 weeks apart. If after 6 doses of lomustine, in the judgment of the treating physician, it is felt that the patient is benefiting from the treatment, then LY2157299 or placebo treatment may be continued after approval by the Lilly CRP until disease progression or unacceptable toxicity occur.

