12.1. Determination of Sample Size

CC1 patients will be entered with the aim of randomizing **CC1** patients to 1 of 3 treatment arms in this multicenter study. The randomization will be in **CC1** (**CC1** patients in LY2157299 monotherapy, **CC1** patients in LY2157299 plus lomustine therapy, and **CC1** patients in lomustine plus placebo therapy).

The primary objective is to compare the OS distributions between of LY2157299 plus lomustine therapy with lomustine plus placebo therapy (control arm) using a Bayesian augmented control design. By incorporating historical information regarding the control group (ie, lomustine plus placebo) into the Bayesian model, it is possible to improve the operating characteristics compared to a standard (frequentist) analysis.

The primary comparison will be considered successful if, after **CC1** patients have completed at least 2 years of follow-up, the posterior probability is greater than **CC1**% that the HR for OS of the combination arm versus lomustine plus placebo is <1.

The study is designed to observe approximately **CC1** events. Simulations (FACTS v2.4) assuming the following were carried out:

- Exponential survival model using summary hazard rates from 2 previous lomustine trials (Study H6Q-MC-JCBF [data on file and Wick et al. 2010a], Batchelor et al. 2010a;) along with data from the lomustine plus placebo arm in this study.
 - The average median OS time is 8.5 months giving an average control hazard rate across these 2 studies of **CC1** week
 - The fixed prior distribution for the control hazard rate has a mean of **CC1** and a weight of **CC1** (weak prior)
- The prior distribution of the log HR between the combination arm and lomustine plus placebo is assumed to be Normally distributed with a mean of zero and a standard deviation of 100 (weak prior)
- A 'true' OS HR of **CC1**
- Patients are randomized in a **CC1** ratio (favoring the LY2157299 plus lomustine arm)
- Enrollment rate is **CC1** patients/month (**CC1** patients/week)
- Minimum follow-up for last subject is approximately 2 years (94 weeks)

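### As visibly marked, the Attachment 1 schedule tables conflict with the protocol text on the number of lomustine doses and, in continued access, on their interval and the blood counts beside them

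*Protocol*

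**What the plan says.** On the number of doses, Protocol Section 8.1 states: "The planned treatment with lomustine will be limited to 6 administrations". Section 9.5 says: "The intended treatment for lomustine is 6 doses, each given 6 weeks apart", and Section 9.4.1 says the same. Section 9.5 names only LY2157299 or placebo as continuing once six doses have been given. SAP Section 5.1 repeats the limit, and SAP Section 6.13.1 uses six administrations in the planned cumulative lomustine dose.

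On monitoring, Section 9.4.1.1 says: "Blood counts should be monitored weekly and repeat doses of lomustine should be given every 6 weeks". It also withholds a repeat dose until neutrophils and platelets have recovered, and it bases dose adjustment on the nadir counts.

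Attachment 1 carries these visible lomustine marks:
- Cycle 1: Day 7±2.
- Cycles 2, 5, 8 and 11: Day 21±2.
- Cycles 3, 6, 9 and 12: none.
- Cycles 4, 7 and 10: Day 6±2.
- The table headed "Study Schedule for the continued access period only, Protocol H9H-MC-JBAL": Day 6±2 of a single set of columns covering Visits 501-5XX.

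The continued-access table lists physical examination, vital signs, CTCAE, echocardiography, ECG, troponin I and BNP, ECG chemistry and hs-CRP. It has no hematology row. The Comments column of the tables is redacted.

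**The concern.** The tables are working instructions. Section 7.3.1 sends sites to the Study Schedule for every enrolled patient's procedures, Section 8.1.4 tells investigators to follow it until study completion is announced, and Section 5.7.1 refers to Attachment 1 for continued access. A site following the visible marks could give more lomustine than the text plans. In continued access it could also dose more often, from a table that does not show the counts the text makes a condition of repeat dosing. Section 9.4.1.1 itself gives delayed hematotoxicity as the reason for the spacing, so this is a patient-safety question. There is a smaller analytic effect: the SAP dose-intensity denominator assumes six doses, and on-study doses beyond six would push the percentage up.

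**Working it through.** **Inputs.** First lomustine dose on Cycle 1 Day 7 and cycle length 28 days (Section 8.1); interval 42 days and six doses (Sections 9.4.1 and 9.5); lomustine stopped if it cannot be given for 12 weeks, i.e. 84 days (Section 9.4.1.1); minimum follow-up of 94 weeks for the last patient (Section 12.1); lomustine marks from Attachment 1.

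**Step 1: the text's own schedule.** Six doses at 7 + 42k, k = 0 to 5, fall on days 7, 49, 91, 133, 175 and 217. The sixth is Cycle 8 Day 21, at 217 / 7 = week 31.

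**Step 2: the on-study marks.** Study day = 28 × (cycle − 1) + day in cycle.

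| Slot | Cycle, day | Marked study day | 7 + 42k |
|---|---|---|---|
| 1 | C1 D7 | 7 | 7 |
| 2 | C2 D21 | 49 | 49 |
| 3 | C4 D6 | 90 | 91 |
| 4 | C5 D21 | 133 | 133 |
| 5 | C7 D6 | 174 | 175 |
| 6 | C8 D21 | 217 | 217 |
| 7 | C10 D6 | 258 | 259 |
| 8 | C11 D21 | 301 | 301 |

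Count: 1 + 4 + 0 + 3 = 8 slots, two more than six. The gaps are 42, 41, 43, 41, 43, 41 and 43 days, and every slot lies within one day of exact six-week spacing, inside the ±2-day windows. The on-study tables therefore agree with the text on interval and differ from it only on count.

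**Step 3: continued access as printed.** One mark per 28-day cycle gives a nominal interval of 28 days. Stretching both ±2-day windows gives at most 28 + 4 = 32 days, still 10 short of 42. The implied frequency is 42 / 28 = 1.5 times that in the text, and no end is visible.

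**Step 4: could doses remain at continued access?** With the longest permitted gap every time, the sixth dose falls by 7 + 5 × 84 = day 427, i.e. 427 / 7 = week 61. The follow-up assumed in Section 12.1 is 94 weeks, or 658 days. If study completion comes no earlier than that, all six doses have been given, or lomustine has been stopped, with 658 − 427 = 231 days to spare. The few days between randomization and first dose do not change this.

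**Step 5: dose intensity.** SAP Section 6.13.1 divides the cumulative dose by six times the Cycle 1 dose. Eight doses at the Cycle 1 level would give 8 / 6 = 133%.

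**The case against.** Four arguments on the other side carry weight.

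First, the redacted Comments columns are the natural place for a dose cap, a spacing note or a restriction to certain patients, above all for a generic cycle covering all Visits 501-5XX. A reader might infer that the plan has no such qualifier. The documents do not support that, because redacted content is not missing content. This stands and limits the finding to the visible marks.

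Second, a slot is not a dose. A patient whose doses have slipped by 258 − 217 = 41 days in total reaches dose six at the Cycle 10 slot, and one who has slipped by 301 − 217 = 84 days reaches it at the Cycle 11 slot. Section 9.4.1.1 permits delays of that size. The grid may simply leave room for late patients, so it does not follow that the protocol authorizes eight doses. What remains is that the visible tables do not say so, and the slots line up with on-time dosing.

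Third, it is tempting to say that every permitted dose is past before continued access opens. That is conditional. Section 8.1.4 also lets completion follow a redacted number of survival events, and 94 weeks is a simulation assumption.

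Fourth, a missing hematology row does not show that the counts are switched off. Section 8.1.3 has investigators perform other tests needed for care, at their discretion, and the on-study cycle tables show hematology only once per cycle (Day 26±2), so the weekly rule always rested on the text. This softens the point. It does not remove it: a schedule that leaves choice and timing of tests to the site still sits beside a rule that sets a weekly frequency and ties repeat dosing to the result.

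**Conclusion.** The visible marks conflict with the text and need reconciling. The on-study tables show eight lomustine slots against a limit of six; the surplus is the Cycle 10 and Cycle 11 slots, which are doses seven and eight only for a patient dosed on time. The continued-access table, read literally, conflicts with both the 42-day interval and the six-dose limit, and with Section 9.5 on what continues after six doses. The absent hematology row is a lesser, partly answered inconsistency.

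A reader might also infer that the on-study slots break the six-week interval; Step 2 shows they reproduce it. Nor should the dose-intensity effect be extended to continued access: Protocol Section 8.1.1 excludes that period from the study treatment period, and SAP Section 6.8 summarizes dose intensity for the treatment period. The 133% figure is the most that on-study slots could produce at the Cycle 1 dose level.

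The conclusion assumes that the marks stand in the columns where they appear and that no redacted comment qualifies them. The discrepancy merits correction because sites work from these tables. It does not bear on the primary survival comparison as designed.

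**What to change.** Check the unredacted Comments columns first. If they already state a cap, a spacing or a restriction, confirm that it agrees with the text. Otherwise:
- Reconcile the lomustine marks in Cycles 10 and 11 and in the continued-access table with Sections 8.1, 9.4.1 and 9.5, on both number of doses and interval.
- Reconcile the continued-access test list with Sections 8.1.3 and 9.4.1.1 on blood counts.
- If the reconciled number of administrations differs from six, bring the planned-dose formula in SAP Section 6.13.1 into line.

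No position is taken on which dosing or monitoring rule is right; that is for the sponsor's clinical team. The cost is a protocol clarification touching three schedule tables and a notice to sites. Sample size and the survival analysis are unaffected.
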